## Measurement Occurrence Chart

Data Collection Instrument	Baseline (1)	Wk1 (2)	Wk2 (3)	Wk3 (4)	Wk4 (5)	Wk5 (6)	Wk6 (7)	Wk9 (8)	Wk13 (9)	M1FU (10)
Screening Questionnaire (survey)										
Session Status (survey)										
Med Given (survey)		✓	✓	✓	✓	✓	✓	✓	✓	✓
CO Level	✓	✓	✓	✓	✓	✓	✓	✓	✓	✓
Cotinine Test	✓	✓	✓	✓	✓	✓	✓	✓	✓	✓
Pregnancy Test	✓				✓		✓	✓	✓	
Urine Drug Screen	✓									
Mini International Neuropsychiatric Interview Mini	✓									
Demographic Form (survey)	↓									
NRT Adherence (survey)		↓	↓	↓	↓	↓	↓	↓	↓	↓
Minnesota Nicotine Withdrawal Scale Pre (survey)	↓	↓	↓	↓	↓	↓	↓	↓	↓	↓
Questionnaire Of Smoking Urges Short Form Pre (survey)	↓	↓	↓	↓	↓	↓	↓	↓	↓	↓
Smoking History Form (survey)	↓									
Weekly Smoking Behavior	✓	✓	✓	✓	✓	✓	✓	✓	✓	✓
Thoughts About Abstinence (survey)	↓	↓	↓	↓	↓	↓	↓	↓	↓	↓
Fagerstrom Test For Nicotine Addiction (survey)	↓					↓	↓	↓	↓	↓
Perceived Stress Scale (survey)	↓	↓	↓	↓	↓	↓	↓	↓	↓	↓
Wisconsin Inventory of Smoking Dependence Motives (survey)	↓					↓	↓	↓	↓	↓
Treatment Expectations (survey)	↓	↓	↓	↓	↓	↓	↓	↓	↓	↓
Smoking Abstinence Questionnaire (survey)	↓					↓	↓	↓	↓	↓
Abstinence Related Motivational Engagement ARME (survey)	↓	↓	↓	↓	↓	↓	↓	↓	↓	↓
Attitudes About Nicotine Replacement Therapy (survey)	↓	↓	↓	↓	↓	↓	↓	↓	↓	↓
Treatment Satisfaction Survey (survey)						↓		↓	↓	↓
Credibility Expectancy Questionnaire CEQ (survey)						↓		↓	↓	↓
Symptom Side Effects (survey)	↓	↓	↓	↓	↓	↓	↓	↓	↓	
Barratt Impulsivity Scale	✓									
Pittsburgh Sleep Quality Index	✓	✓	✓	✓	✓	✓	✓	✓	✓	✓
Minnesota Nicotine Withdrawal Scale Post (survey)	↓	↓	↓	↓	↓	↓				
Questionnaire Of Smoking Urges Short Form Post (survey)	↓	↓	↓	↓	↓	↓				
Alliance Questionnaire						✓				
Alliance Questionnaire Therapist						✓				
Group Assignment (survey)										
Audio Recording Length		✓	✓	✓	✓	✓				

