**appointment). Wait to give the gum to the participant until the session is being recorded.**

5. Have the participant fill out all of the questionnaires related to the session in REDCap, **except the Credibility Expectancies Questionnaire, the SECOND Minnesota Nicotine Withdrawal Scale and the SECOND Questionnaire of Smoking Urges.**
6. While the participant is filling out the questionnaires on REDCap, have REDCap open on the desktop and double check for participant entry errors as they progress through the questionnaires.
7. Tell the client that you are about to start the recording for the session. Explain that “this is a manualized intervention; therefore it will not feel like traditional therapy. We will be working from a manual and will adhere to the manual content, exclusively.”
8. Turn on the recording and **state your name, the date, and the time that you are starting the therapy. Do your best not to say the participant’s name while being recorded.**
9. Give the participant the assigned client Intervention workbook and tell them to follow along as you go through your Therapist Intervention Manual. Let them know that the counseling could take up to 30 minutes and **they are urged to write down information in their workbooks.**
10. When appropriate, pause the audio recording and have the participant fill out the following:
  - **The second Minnesota Nicotine Withdrawal Scale**
  - **The second Questionnaire of Smoking Urges**
    - **Based on the participant’s response to the Minnesota Nicotine Withdrawal Scale and the Questionnaire of Smoking Urges, graph the before and after scores in their workbook.**
11. Un-pause the audio recording and continue the intervention by going over the participant’s before and after scores for the Minnesota Nicotine Withdrawal Scale and Questionnaire of Smoking Urges.
12. Go over the Tobacco Use and NRT Use calendars.
13. Provide them with the copies of the calendars (in their folder) to keep in their pocket/wallet for use when they do not have their manual with them.
14. After the therapy, ask the participant if they have any questions. If they do not, tell them you are ending the recording.
15. Schedule the next appointment for the following week (preferably the same day of the week and the same morning time). **Once you have it scheduled, make sure the appointment is placed on your UABMC calendar, desk calendar, and recorded in the REDCap Calendar application.**

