## **Week 2**

1. Check to see if any information on participant's contact sheet needs to be updated.
2. Administer the CO test. Refer to the CO directions under the "CO Monitor" section on **Page 8** of this manual. Record the CO level in REDCap.
  - If the CO level is 3 or below, you need to administer a urine cotinine test to confirm that the participant is using nicotine products.
3. Collect the participant's Tobacco Use and NRT Use calendars and enter the data for the previous week into the appropriate SPSS database, then return the calendars to the participant.
4. Collect the used nicotine patches and gum packages and dispose of them after reviewing the calendars. Any unused patches/gum packages can be given back to the participant.
5. Gather either the 21 mg patch or the 14 mg patch and give it to the participant. **Patch dosage is based on number of cigarettes smoked determined at Baseline appointment. Be sure to write down the time that the patch is placed on their arm. Ideally, the participant should have the patch on for 30 minutes before the intervention begins.**
6. Gather the inhaler box and give it to the participant to use. **Wait to give the inhaler to the participant until the session is being recorded.**
7. Have the participant fill out all of the questionnaires related to the session in REDCap, **except the SECOND Minnesota Nicotine Withdrawal Scale and the SECOND Questionnaire of Smoking Urges.**
8. While the participant is filling out the questionnaires on REDCap, have REDCap open on the desktop and double check for participant entry errors as they progress through the questionnaires.
9. Tell the client that you are about to start the recording for the session. Explain that "this is a manualized intervention; therefore it will not feel like traditional therapy. We will be working from a manual and will adhere to the manual content, exclusively."
10. Turn on the recording and **state your name, the date, and the time that you are starting the therapy. Do your best not to say the participant's name while being recorded.**

11. Tell the participant to follow along in their client Intervention workbook as you go through your Therapist Intervention manual. Let them know that the counseling could take up to 30 minutes and **they are urged to write down information in their workbooks.**
12. When appropriate, pause the audio recording and have the participant fill out the following:
  - **The second Minnesota Nicotine Withdrawal Scale**

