## Intervention Group B

### Week 1

1. Check to see if any information on participant's contact sheet needs to be updated.
2. Administer the CO test. Refer to the CO directions under the "CO Monitor" section on Page 8 of this manual. Record the CO level in REDCap.
  - If the CO level is 3 or below, you need to administer a urine cotinine test to confirm that the participant is using nicotine products.
3. Gather either the 21 mg patch or the 14 mg patch and give it to the participant. (Patch dosage is based on number of cigarettes smoked determined at Baseline appointment). Be sure to write down the time that the patch is placed on their arm. Ideally, the participant should have the patch on for 30 minutes before the intervention begins.
4. Gather the 4mg or 2mg nicotine lozenge and give it to the participant to use. (Lozenge dosage is based on how soon participant smokes their first cigarette after waking, as reported at Baseline appointment). Wait to give the lozenge to the participant until the session is being recorded.
5. Have the participant fill out all of the questionnaires related to the session in REDCap, except the Credibility Expectancies Questionnaire, SECOND Minnesota Nicotine Withdrawal Scale and the SECOND Questionnaire of Smoking Urges.
6. While the participant is filling out the questionnaires on REDCap, have REDCap open on the desktop and double check for participant entry errors as they progress through the questionnaires.
7. Tell the client that you are about to start the recording for the session. Explain that "this is a manualized intervention; therefore it will not feel like traditional therapy. We will be working from a manual and will adhere to the manual content, exclusively."
8. Turn on the recording and state your name, the date, and the time that you are starting the therapy. Do your best not to say the participant's name while being recorded.
9. Give the participant the assigned client Intervention workbook and tell them to follow along as you go through your Therapist Intervention Manual. Let them know that the counseling could take up to 30 minutes and they are urged to write down information in their workbooks.
10. When appropriate, pause the audio recording and have the participant fill out the following:
  - **The second Minnesota Nicotine Withdrawal Scale**
  - **The second Questionnaire of Smoking Urges**

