## Control Group

### Week 1

1. Check to see if any information on participant's contact sheet needs to be updated.
2. Administer the CO test. Refer to the CO directions under the "CO Monitor" section on **Page 8** of this manual. Record the CO.
  - If the CO is 3 or below, you need to administer a urine cotinine test to confirm that the participant is using nicotine products.
3. Have the participant fill out all of the questionnaires related to the Session in REDCap, **except the SECOND Minnesota Nicotine Withdrawal scale, and the SECOND Questionnaire of Smoking Urges.**
4. While the participant is filling out the questionnaires on REDCap, have REDCap open on the desktop and double check for participant entry errors as they progress through the questionnaires.
5. Tell the client that you are about to start the recording for their session. Explain that "this is a manualized intervention; therefore it will not feel like traditional therapy. We will be working from a manual and will adhere to the manual content, exclusively."

6. Turn on the recording and state your name, the date, and the time that you are starting the therapy. Do your best not to say the participant's name while being recorded.
7. Give the participant the assigned client Control workbook and tell them to follow along as you go through your therapist control manual. Remind them that the counseling could take up to 30 minutes and they are urged to write down information in their workbooks.
8. **Make sure that you have gone over the Tobacco Use calendar before you finish the recording.** Provide them with copies of the calendar to keep in their pocket/wallet for use when they do not have their manual. Ask that they bring back the calendar and workbook to each visit.
9. After the therapy ask the participant if they have any questions. If they do not, tell them you are ending the recording.
10. Have the participant complete the remaining session measures (Credibility Expectancies Questionnaire, second Minnesota Nicotine Withdrawal Scale, and second Questionnaire of Smoking Urges).
11. Schedule the next appointment for the following week (preferably the same day of the week and same time). Once you have it scheduled, make sure the appointment is placed in the [name] Lab Google Calendar.
12. Compensate the participant on their Greenphire ClinCard.
13. Give the participant an appointment card.

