- **Wisconsin Inventory of Smoking Dependence Motives:** Subject fills out form within REDCap Survey Queue. Verify form is completed before allowing participant to leave. **Completed at Baseline, Week 5, Week 6, Week 9, Week 13, and Month 1 Follow-up.**

- **Attitudes About Nicotine Replacement Therapy:** Subject fills out form within REDCap Survey Queue. Verify form is completed before allowing participant to leave. Completed at all visits.
- **Abstinence-Related Motivational Engagement (ARME):** Subject fills out form within REDCap Survey Queue. Verify form is completed before allowing participant to leave. Completed at all visits.
- **Smoking Abstinence Questionnaire (SAQ):** Subject fills out form within REDCap Survey Queue. Verify form is completed before allowing participant to leave. Completed only at Baseline, Week 5, Week 6, Week 9, Week 13, and Month 1 Follow-up.
- **Symptoms/Side Effects Scale:** Subject fills out form within REDCap Survey Queue. Verify form is completed before allowing participant to leave. Completed at all visits, except Month 1 Follow-up.
- **Treatment Expectations:** Subject fills out form within REDCap Survey Queue. Verify form is completed before allowing participant to leave. Completed at all visits.
- **Treatment Satisfaction Survey:** Subject fills out form within REDCap Survey Queue. Verify form is completed before allowing participant to leave. Completed only at Week 5, Week 13, and Month 1 Follow-up.
- **Credibility Expectancy Questionnaire (CEQ):** Subject fills out form within REDCap Survey Queue. Verify form is completed before allowing participant to leave. Completed only at Week 5, Week 13, and Month 1 Follow-up.
- **Minnesota Nicotine Withdrawal Scale 2:** Subject fills out form within REDCap Survey Queue. Verify form is completed before allowing participant to leave. Completed only at Week 1, Week 2, Week 3, Week 4, and Week 5.
- **Questionnaire of Smoking Urges-Short Form 2 (QSU):** Subject fills out form within REDCap Survey Queue. Verify form is completed before allowing participant to leave. Completed only at Week 1, Week 2, Week 3, Week 4, and Week 5.
- **Alliance Questionnaire:** Subject fills out form within REDCap Survey Queue. Verify form is completed before allowing participant to leave. Completed only at Week 5.

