NRT Adherence	X	X	X	X	X	X	X	X	X	

Note: BL=Baseline Assessment; S=session; WK=week; M=month; PS=Product Selection; ¹All participants will complete these surveys twice (at the beginning and end of session) during sessions 1-4.

Randomization. We anticipate enrolling 10 pre-pilot participants in 3 months and 80 participants in 20 months and, based on our previous study with this population, expect to retain at least 70% through the one month follow-up point. Randomization will occur after completion of the initial screening and assessment.

Primary Outcomes. Feasibility and acceptability will be measured through high study retention (70%) and recruitment (recruitment of all participants within 24 months) in our groups. Additional items of acceptability include high scores on treatment satisfaction and credibility/expectancies that are equal or higher to the SC

group. Medication adherence is a third primary outcome with expected differences between our groups. Adherence is notoriously difficult to determine. Self-reported adherence is not always reliable, particularly during treatment studies where there is a demand characteristic to report the desired targeted behavior⁷³⁻⁷⁴ (e.g., adherence to NRT). The behavioral methods described under the assessment section represent the best available self-report tools for determining NRT adherence (e.g., TLFB report, returning used NRT patches and used product blister packs/packaging). Adherence will be defined by self-report using the TLFB and verified through returned patches and packaging. Good adherence is defined by taking greater than 80% of doses of medication at each time point. We have used these techniques in previous studies with low income populations with good compliance for use of TLFB verified by return of NRT materials⁷⁵.

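### The control step lists for Weeks 1 to 4 give a Credibility/Expectancy Questionnaire that no schedule places there and no In vivo list gives, and the SAP names no visit for the between-arm test

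*Protocol*

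**What the plan says.** **Control step lists (Protocol, Therapy Protocol, Control Group).** After the session, Week 1 step 10 and step 11 of Weeks 2, 3 and 4 carry the same instruction: "Have the participant complete the remaining session measures (Credibility Expectancies Questionnaire, second Minnesota Nicotine Withdrawal Scale, and second Questionnaire of Smoking Urges". The pre-session step in the same lists asks for all session questionnaires "except the SECOND Minnesota Nicotine Withdrawal scale, and the SECOND Questionnaire of Smoking Urges", so it does not hold the CEQ back.

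**In vivo step lists, Week 1.** Step 5 for Group A asks for all session questionnaires "except the Credibility Expectancies Questionnaire, the SECOND Minnesota Nicotine Withdrawal Scale and the SECOND Questionnaire of Smoking Urges". Groups B, C and D make the same exception in almost the same words (Group B: "except the Credibility Expectancies Questionnaire, SECOND Minnesota Nicotine Withdrawal Scale and the SECOND Questionnaire of Smoking Urges"). Step 10 then gives only the second withdrawal scale and the second urges questionnaire. No later step gives the CEQ.

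**In vivo step lists, Weeks 2 to 4.** The pre-session exception reads "except the SECOND Minnesota Nicotine Withdrawal Scale and the SECOND Questionnaire of Smoking Urges". The CEQ is not mentioned.

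**Schedules.** Data Collection Parameters in the protocol says of the CEQ: "Completed only at Week 5, Week 13, and Month 1 Follow-up". SAP Table 2 marks the same three visits. The protocol's Measurement Occurrence Chart marks those three and Week 9. None of the three marks Weeks 1 to 4.

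**Use in the analysis.** Under Primary Outcomes, the SAP lists among the additional items of acceptability "high scores on treatment satisfaction and credibility/expectancies that are equal or higher to the SC" group. The Aim 2 analysis compares credibility and expectancy between the groups by t-test and names no visit.

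**The concern.** The step lists are what staff work from at the visit. Read as written, they add CEQ ratings in one arm at weeks when no schedule has the form. Two consequences follow for the between-arm comparison.

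- **Prior exposure.** At Week 5, a control could be rating the treatment for the fifth time and an In vivo participant for the first. Repeated rating may itself move scores, and the arms would differ in it.
- **Stray data.** Any Week 1 to 4 control ratings would sit in the same database as the scheduled ones. Because the SAP names no visit for the t-test, nothing in it keeps them out of an average over visits or a pooled comparison.

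The measure is an acceptability item under Primary Outcomes, although retention and recruitment come first there and credibility and expectancy appear among the additional items.

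**Working it through.** The plan states no figure to reproduce. The check is a cross-reading of the step lists against the three schedules, followed by a count per participant who attends every visit.

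**Step 1. Where the CEQ appears**

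| Source | Weeks 1–4 | Week 5 | Week 9 | Week 13 | One-month follow-up |
|---|---|---|---|---|---|
| Data Collection Parameters | no | yes | no | yes | yes |
| SAP Table 2 | no | yes | no | yes | yes |
| Measurement Occurrence Chart | no | yes | yes | yes | yes |
| Control step lists | named after each of 4 sessions | not held back | common list | common list | common list |
| In vivo step lists (A–D) | held back at Week 1 and not given later; not named at Weeks 2–4 | not held back | common list | common list | common list |

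At Week 5 all five lists hold back the same three forms: the Alliance Questionnaire, the second withdrawal scale and the second urges questionnaire. The CEQ therefore falls in the pre-session set in both arms. Weeks 9 and 13 and the follow-up each have one list for all participants.

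**Step 2. Count with the lists followed as written and the form available**

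Total = unscheduled ratings at Weeks 1–4 + scheduled ratings.

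- Three-visit schedule: control 4 + 3 = 7; In vivo 0 + 3 = 3.
- Chart schedule, with Week 9: control 4 + 4 = 8; In vivo 0 + 4 = 4.
- Difference on either schedule: 4, all of it before Week 5.

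**Step 3. How the count depends on REDCap**

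The Survey Queue section says questionnaires load automatically for the visit attended. The set-up of the queue is not shown, so I take it as an assumption and give the range on the three-visit schedule.

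- Queue follows the schedules and nobody opens the form by hand: control 0 + 3 = 3; In vivo 0 + 3 = 3; difference 0.
- Queue loads the CEQ at Weeks 1–4 in both arms, each control completes it once per session, and In vivo completes it before the session at Weeks 2–4 under the general instruction: control 4 + 3 = 7; In vivo 3 + 3 = 6; difference 1, with different timing around the session.
- Form reaches controls only, through an arm-specific queue or by hand: 7 against 3; difference 4.

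The excess in control thus lies between 0 and 4 ratings per participant. The documents do not say where in that range the trial falls.

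**Step 4. Internal consistency of the control list**

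In Week 1, step 3 does not hold the CEQ back, yet step 10 treats it as still outstanding. The list therefore conflicts with itself as well as with the schedules.

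**The case against.** The strongest reply is that this is leftover text with no effect on the data. All three schedules omit Weeks 1 to 4, REDCap loads surveys by visit, and a queue built from any of those schedules would show no CEQ to controls at those weeks. The In vivo Week 1 exception with nothing following it, and the conflict within the control list, both look like remnants of another schedule. This has force: it means the count of 7 against 3 is conditional. It does not remove the point. The queue set-up is not shown, the Baseline procedures speak of questionnaires for the assigned group (so a queue common to all arms cannot be assumed), and the instruction appears in four separate control lists.

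A second reply is that the scheduled ratings are collected in the same way in both arms. That is correct. A reader might infer from the step lists that a primary acceptability measure is collected differently by arm throughout. The documents do not support that: the handling at Week 5 is identical in all five lists, and the later visits share one list.

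Two further inferences also fail. Rating a treatment delivered by one continuing therapist is not peculiar to controls, because the Therapy Protocol asks for the same staff member across the five weekly sessions for every participant. Nor is it a bias in collection that In vivo participants first rate after four weeks of product use. That experience is the treatment whose acceptability is being measured.

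**Conclusion.** The point holds in a limited form. The control lists for Weeks 1 to 4 and the In vivo lists for Week 1 contradict every CEQ schedule in the two documents, and the schedules disagree among themselves on Week 9. If staff follow the lists and REDCap does not block the form, controls complete up to four extra CEQs before Week 5 (7 against 3, or 8 against 4 on the chart).

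What is at risk is unequal prior exposure at the first common rating, and Week 1 to 4 control ratings entering a t-test with no stated visit. The size of any effect on scores cannot be derived from the documents. The conclusion rests on the step lists as written; whether the extra ratings were actually taken depends on a REDCap configuration that neither document shows. It is a drafting inconsistency worth correcting because it touches an acceptability item under Primary Outcomes. It does not show that the comparison at the scheduled visits is biased.

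**What to change.** 1. In the protocol, delete the CEQ from the control post-session steps at Weeks 1, 2, 3 and 4, and from the Week 1 pre-session exception in In vivo Groups A to D.
2. Reconcile the Measurement Occurrence Chart, which marks Week 9, with Data Collection Parameters and SAP Table 2, which do not, so that both arms share one CEQ schedule. Check that the REDCap queue matches it.
3. In the SAP, state that the between-arm t-test of credibility and expectancy uses only the common visits, and name the visit for the comparison, for example Week 5. State also that any Week 1 to 4 control ratings already collected are excluded.

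The cost is a few lines of protocol text and a short addition to the SAP. It reduces the burden on controls if the extra forms were being given. The downside is that there will be no early credibility rating; the current step lists do not provide one for In vivo either. If data collection is already complete, the SAP addition still keeps the stray ratings out of the comparison. It cannot undo any unequal prior exposure, so the report should state how many Week 1 to 4 CEQs exist in each arm.
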